8.0 Research Plan and Procedures

8.1 HYPOTHESIS: Describe the hypothesis or what the study hopes to prove:

We hypothesize that couples in the intervention condition will have lower Composite Risk for HIV (CR-HIV) at 12-month follow-up compared to couples in the control condition.

8.2 AIMS: List the specific aims:

The primary specific aim is to:

1. Evaluate the efficacy of the T2 couples HIV counseling intervention on Composite Risk for HIV (CR-HIV) compared to an enhanced standard of care (SOC) control condition.

The secondary aims are to:

1. Assess the effects of the T2 couples HIV counseling intervention on theory-based mediators (i.e. couples' self-efficacy, communication and joint problem-solving skills, coping with gender-based minority stress and social oppression).
2. Explore partner gender, couple HIV status (seroconcordant negative/seroconcordant positive /serodiscordant) as moderators of the effect of the intervention on CR-HIV.

8.3 DESIGN: Briefly describe the study design (e.g., observational, interventional, randomized, placebo-controlled, blinded, cross-over, cross-sectional, longitudinal, pharmacokinetic, etc.):

Using a two-arm randomized controlled trial (RCT) design, we will examine intervention effects on Composite Risk for HIV (CR-HIV) at 12-month follow-up comparing couples randomized to the intervention versus an enhanced standard of care (SOC). To achieve these aims, we will recruit and randomize 54 couples (108 participants) to test a theory-based couples-focused intervention that addresses within-couple and extra-dyadic sexual risk, structural factors related to risk, routine testing for HIV and other sexual transmitted infections (STI), preexposure prophylaxis (PrEP) uptake and adherence, and antiretroviral therapy (ART) adherence (for couples in which one partner is HIV-positive).

After completing baseline surveys, couples are randomized (stratified by couple serostatus at enrollment) to the intervention or enhanced standard of care using a computerized secure and fraud-resistant procedure employed in our teams prior studies. UCF has used this method in several RCTs; our experience with over 700 participants indicates that it is successful in achieving balance across demographic, mediating, and outcome variables.

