4. CR-HIV (primary outcome) is a couple-level binary indicator of any HIV risk (e.g., yes=1 vs. no=0), which is an algorithm based on whether one or both partners report condomless anal or vaginal sex with a HIV serodiscordant or status-unknown primary or other partner in the past 3 months. Couples are coded as 0 if neither partner reports condomless anal or vaginal sex. If one or both partners in the dyad report condomless sex with a serodiscordant or status-unknown primary or other partner, then the couple is coded as 1 if (i) the HIV-negative participant is not adherent to PrEP and/or (ii) the HIV-positive participant is not virally suppressed. Sexual risk behavior will be measured using the assessment that we have used in our previous studies to explore the number of occasions of different sexual acts (vaginal, anal; receptive, insertive) with three different types of partners (primary partner, casual partner, paying partner), use of condoms during the past 3 months, and knowledge about partners' HIV status. Assessments ascertain sexual behaviors with non-trans male, non-trans female, and transgender partners, and will be asked at each follow-up. At-risk sex will be defined as any vaginal or anal intercourse without condoms that occurs with a person of known positive or unknown serostatus during the follow-up period. Of the participants who report condomless sex with a serodiscordant or unknown serostatus partner, we will attempt to assess PrEP use using dried blood spot (DBS) procedures for biological measurement of adherence from tenofovir diphosphate concentrations in blood plasma. We will use dosing categories for quantification similar to those used in past drug-level studies of PrEP adherence, allowing us to estimate the number of tablets participant are taking per week (e.g., 700-1249 fmol for 4-6x per week and > 1250 for daily dosing). HIV-positive participants will have their blood drawn at each follow-up visit to determine viral suppression. Viral suppression is indicated by an undetectable HIV-1 level on the COBAS® AmpliPrep/COBAS® TaqMan® HIV test kit (Roche Molecular Systems, Inc.), which has a threshold for undetectability = < 20 copies/mL and is conducted at each follow-up assessment visit. Our secondary outcomes include self-report HIV and STI testing over the 12 months of follow-up.

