Auxiliary variables will be included to help meet the MAR assumption;^{88, 89} sensitivity analyses will be conducted with weighted MI to assess the MAR assumption's robustness⁹⁰ using SAS⁹¹ and Mplus.

Primary analyses to address Primary Specific Aim 1. If the CHIP intervention is successful, a lower proportion of intervention participants will engage in CR-HIV relative to control group participants following intervention exposure. Therefore, to address Specific Aim 1 we hypothesize that the odds of CR-HIV will be lower for CHIP participants than for control participants (Hypothesis 1). Our primary interest is to estimate the marginal or population-average effects of CHIP exposure on CR-HIV rather than the effect for a hypothetical average subject or couple.⁹² Moreover, within-subject and within-couple CR-HIV correlations are nuisance parameters rather than quantities of interest to be modeled explicitly. Finally, the statistical literature indicates the superior performance of generalized estimating equations (GEE) relative to generalized linear mixed models (GLMMs) for the analysis of dyadic data with categorical outcomes such as CR-HIV.⁹³ Accordingly, we will use GEE for the proposed primary analysis to test Hypothesis 1 by a planned time-averaged comparison of post-baseline measurements of CR-HIV from the intervention group with the post-baseline measures of CRHIV from the control group. Alpha (α) will be set at .05 for this planned comparison. Any additional post-hoc comparisons (e.g., paired comparisons of groups at each time point) will maintain nominal alpha of .05 through the use of simulation-based stepdown multiple comparison methods.⁹⁴ The alternating logistic regression (ALR) approach implemented in SAS PROC GENMOD will be used to address the 3-level clustering of observations within participants and participants within dyads. Though GEE estimates are consistent even if the correlation structure is misspecified, GEE's statistical efficiency improves as the working correlation structure more closely approximates the actual correlation structure;⁹⁵ therefore, various correlation structures suitable for the study's design will be considered (e.g., exchangeable; nested-1).⁹⁶ The QIC statistic will be used to select the final correlation structure.⁹⁷ Couple serostatus will be included as a covariate as required by the stratified randomized design.⁹⁸ Additional relevant covariates such as relationship length, as well as intersectionality criteria and structural drivers (e.g., age, race/ethnicity, poverty, unemployment) will be included if they improve QIC. We will use Robust Huber-White "sandwich" standard errors to obtain correct inferences even if the chosen correlation structure remains slightly misspecified.

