11.0 Sample Size and Eligibility Criteria

11.1 ENROLLMENT TARGET: How many people will you enroll:

108

If there are multiple participant groups, indicate how many people will be in each group:

Control condition: 54 participants / 27 dyads

11.3 SAMPLE SIZE JUSTIFICATION: Explain how and why the number of people was chosen. For multi-site studies, this is referring to the number that will be enrolled across all sites:

Power analyses were generated using the two-group repeated proportions module in NCSS PASS 15104 to compute minimum detectable effect sizes for the primary analysis to address Hypothesis 1. Our pilot study found standardized effect sizes ranging from .38 to .42,¹⁶ so we powered our study to detect similarly-sized effects in worst-case scenarios where within-participant clustering of outcomes are substantial. The study will begin with 200 participants from 100 couples evenly assigned to the intervention and control groups. Assuming 20% attrition, data from 160 participants from 80 couples will be available for analysis at all time points. Due to the clustered nature of the dyadic data, observations from participants who belong to the same couple will be correlated. In m-PI [name]'s previous study of 190 TW and their male partners, for instance, the average within-couple correlation of sexual risk measurements was $r=.$ 07. Accordingly, we lowered the effective sample size (ESS) input for the power analyses to be $ESS= N/DEFF$, where DEFF is the design effect or variance inflation attributable to using correlated data. DEFF is computed as $1+(M-1)*r$, where M is the number of participants per dyad (i.e., two). Therefore $DEFF=1+(2-1)*.07=1.07$, so $ESS=160/1.07=149$. Assuming, $\alpha=.05$, power=.80, and $ESS=149$, we computed the minimum detectable odds ratio (OR), proportion difference (pdiff), and standardized proportion difference (h) for the proposed time-averaged comparisons, assuming four post-baseline measurements and a wide range of CR-HIV base rates P_0 for levels of risk for TW and their partners seen in the literature.^{4,5,20} Since the within-subject correlation ρ for repeated measures is unknown, we varied it across a wide range from .20 to .80 (see Table 2). The obtained minimum detectable effect size estimates are similar to or smaller than those detected in our pilot study, suggesting that our study is sufficiently powered to test primary Hypothesis 1.

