Original Power Calculations. Originally, our sample size of 100 couples would allow us the statistical power to engage in meaningful comparisons between the two intervention arms. We assumed the 200 participants from 100 couples will be evenly assigned to the intervention arms: 50 couples in intervention and 50 couples in control. Assuming 20% attrition, data from 160 participants (80 couples) would have been available for analysis at all time points (i.e., 3-, 6-, 9, 12-month follow up). Using NCSS PASS, we conducted a series of power calculations to determine the maximum sample size requested to address the primary study aims. We computed the minimum detectable odds ratio (OR), proportion difference (pdiff), and standardized proportion difference (h) across our two study arms for the proposed time-averaged comparisons, assuming four post-baseline measurements and a wide range of base proportions for levels of risk for TW and their partners seen in the literature (i.e., 10%-50%). Since the within-subject correlation ρ for repeated measures is unknown, we varied it across a wide range from .20 to .80. Under these conditions, ORs ranged from 0.17 to 0.56, raw proportion differences ranged from 6.6% to 20.5%, and standardized proportion differences (h) ranged from .27 to .42. **Revised Power Calculations.** We repeated the power analysis approach utilized in our proposal submission. The revised power analysis again assumes $\alpha=0.05$, power=0.80, 4 post-baseline measurements, and baseline reference proportions ranging from 0.10 to 0.50. The within-subject correlation for repeated measures was allowed to vary from 0.20 to 0.80. The N of participants was varied from 100 to 200 to illustrate the potential impact of various sample size reductions on the ranges of minimum detectable effect sizes. Conventional benchmarks for effect size are $h=0.20$ for a small effect size, $h=0.50$ for a medium effect size, and $h=0.80$ for a large effect size. Assuming we reach at least 50% of our goal of recruiting 100 couples, under most circumstances we will still be able to detect a small-to-medium effect size. Even under the least advantageous combination of circumstances (recruiting only 50 couples, baseline reference proportions closer to 10%, and very high correlations between repeated measures), a medium-to-large effect size is still detectable.

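### CR-HIV is defined as one value per couple, but the power statement counts participants; with 54 couples the claimed small-to-medium detectability does not hold

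*Combined protocol and SAP*

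**What the plan says.** Section 8.11, item 4, defines the primary outcome: "CR-HIV (primary outcome) is a couple-level binary indicator of any HIV risk". A couple is coded from what one or both partners report. Section 8.1 puts the hypothesis at the same level, predicting that "couples in the intervention condition will have lower Composite Risk for HIV (CR-HIV") at 12 months. Section 8.3 sets the size: "we will recruit and randomize 54 couples (108 participants").

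Section 8.13 changes the unit. It expects that "a lower proportion of intervention participants will engage in CR-HIV relative to control group participants", plans a GEE with visits nested in participants and participants nested in dyads, and later treats CR-HIV as an individual's response.

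Section 11.3 counts participants. It starts from 200, takes off 20% for attrition, and applies a within-couple correlation of .07 observed for sexual-risk measurements in an earlier study: "Therefore $DEFF=1+(2-1)*.07=1.07$, so $ESS=160/1.07=149". It then sets the results against the pilot: "The obtained minimum detectable effect size estimates are similar to or smaller than those detected in our pilot study". From that comparison it draws its conclusion on power, in the words "suggesting that our study is sufficiently powered to test primary Hypothesis 1". The revised calculation is described as repeating this approach with 100 to 200 participants. It concludes that with at least 50 of the 100 couples, "under most circumstances we will still be able to detect a small-to-medium effect size". The approvals of the reduction are recorded immediately afterwards.

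**The concern.** If both partners carry the same CR-HIV value at each visit, their within-couple correlation is 1, not .07. The plan's own formula then gives a design effect of 1 + (2 − 1) × 1 = 2, and the effective sample size is the number of couples. Section 11.3 gives no power figure on that basis.

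The revised sentence is the statistical case for going from 100 couples to 54. If it fails for the outcome as defined, the trial can reliably detect only effects of roughly medium size or more. A null result could then be read as evidence against an effect the trial had little chance of finding. The unsettled unit also leaves the structure of the primary analysis dataset open. Test size is not at issue, because section 8.13 plans for dyad clustering with sandwich standard errors.

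**Working it through.** **Inputs.** From section 11.3: power .80, four post-baseline visits, base rates P0 from .10 to .50, within-subject correlation ρ from .20 to .80, 20% attrition, within-couple r = .07, pilot effects h = .38 to .42, and benchmarks h = .20 (small) and .50 (medium). From section 8.13: alpha .05, taken as two-sided. From section 8.3: 54 couples, 108 participants. The grid is P0 = .1, .2, .3, .4, .5 by ρ = .2, .5, .8, which makes 15 scenarios; these points are chosen within the plan's ranges.

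**Formula.** Time-averaged comparison of two proportions on the log odds ratio, pooled variance, n per arm:

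- SE = √[ 2/(p̄q̄) × (1 + 3ρ)/4 ÷ n ]
- detectable effect: solve |ln OR| = (1.960 + 0.842) × SE for p1 < P0
- h = 2·arcsin√P0 − 2·arcsin√p1
- power = Φ(|ln OR|/SE − 1.960)

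**Step 1: reproduce the plan.** With an effective sample size of 149 (74.5 per arm):

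| | Stated in 11.3 | Obtained |
|---|---|---|
| OR | .17 to .56 | .166 to .556 |
| Difference | 6.6% to 20.5% | 6.6% to 20.4% |
| h | .27 to .42 | .275 to .419 |

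**Step 2: change only the sample counted.**

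- Individual reading: 108 × .8 ÷ 1.07 = 80.7
- Couple, no attrition: 108 ÷ 2 = 54
- Couple, 20% attrition: 54 × .8 = 43.2

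One scenario in full, P0 = .50 and ρ = .5, so (1 + 3ρ)/4 = .625:

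- n = 74.5: p1 = .324, h = .36
- n = 27: p1 = .222, p̄ = .361, SE = √(8.67 × .625 ÷ 27) = .448, |ln OR| = 2.802 × .448 = 1.255, h = .59

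| Basis | Effective n | Detectable h | Above .50 | Above .42 | Power for h .38–.42, P0 ≥ .20 |
|---|---|---|---|---|---|
| Plan, 200 participants | 149 | .27–.42 | 0 of 15 | 0 of 15 | 72–99% |
| 108 participants, attrition, DEFF 1.07 | 80.7 | .35–.56 | 4 of 15 | 9 of 15 | 46–88% |
| 54 couples | 54 | .41–.68 | 9 of 15 | 14 of 15 | 33–73% |
| 54 couples, 20% attrition | 43.2 | .44–.75 | 12 of 15 | 15 of 15 | 28–64% |

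**Step 3: drop the weakest scenarios.** At P0 = .10 the couple-level solutions need an intervention rate of 0.3% to 1.4%. In 27 couples that is fewer than one event per visit (27 × .014 = 0.4), so the formula is not reliable there. With P0 of .20 or more, h is .45–.68 (8 of 12 above .50) for 54 couples and .49–.75 (11 of 12) for 43.2.

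**Step 4: cross-checks.** An arcsine calculation gives power of 33–68% for 54 couples and 27–59% for 43.2. Simulation with one record per couple-visit, a couple-clustered sandwich SE and base rates .2, .3 and .5 (4,000 trials per scenario) gives 25–69% with 27 couples per arm and 17–58% with 21. Simulated test size is 4.4–6.7%. Entering both partners' identical rows within a couple cluster leaves the independence-GEE estimate and its sandwich SE unchanged, so the second row adds no information.

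**The case against.** The strongest reply is that nothing in section 11.3 is miscalculated. Its original figures reproduce, and the analysis it powers, in section 8.13, is written for participants. On that reading 11 of 15 scenarios have h at or below .50, and the quoted sentence is defensible. This stands, and it is why the unit has to be settled first. But section 8.11 defines no participant-level CR-HIV; the only definition given is per couple.

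A second reply is that the revised power table is not shown, so the revised run itself cannot be checked. The text's worst case also fits the formula poorly on the h scale: at P0 = .10 and ρ = .8, 100 participants give h of .43, or .47 after attrition and DEFF, which is below medium. That limits what can be said about how the revised run was made. It does not turn participants into couples, and the worst-case sentence is not challenged here.

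Third, counting scenarios with a cut at .50 is a choice. At 54 couples without attrition several exceed .50 only modestly: 8 of 15 are at or below .55. Complete loss of 20% is also pessimistic, given planned multiple imputation and the 91–93% retention reported in section 15.1 for earlier 12- to 18-month studies. These points soften the size of the shortfall. The majority is still above .50 without any attrition.

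Finally, the claim of sufficient power belongs to the 200-participant design, and the pilot effects are not shown to be on the couple-level outcome. Both are fair. The claim nevertheless remains unlabelled in the justification for a 108-person trial, and .38–.42 is used here only as the plan's own benchmark.

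**Conclusion.** The concern holds. For CR-HIV as section 8.11 defines it, 54 couples detect h of about .41–.68, or .44–.75 with 20% attrition, and most scenarios lie above the plan's medium benchmark. The statement about small-to-medium effects is therefore not supported for the defined outcome. The claim of sufficient power fails on either reading at the current size: detectable h exceeds .42 in 9 of 15 scenarios counting individuals, and in 14 or 15 of 15 counting couples.

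This rests on a two-sided test, base rates of 10–50% carried over to couples (a rate for one or both partners may be higher than an individual rate), attrition shown both ways, and small-to-medium read as h up to .50. The damage is to the stated power and to the clarity of what is being estimated. It must be corrected because it concerns the unit of the primary outcome and the only power justification for the reduced trial.

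**What to change.** State one unit for CR-HIV and use it in sections 8.1, 8.11, 8.13 and 11.3.

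- **If the couple:** restate section 11.3 for 54 couples, h about .41–.68 without attrition and .44–.75 with 20%, and mark the base-rate .10 scenarios as outside the formula's reliable range. Remove the small-to-medium sentence and the 200-participant conclusion. In section 8.13, fit the GEE to one record per couple-visit, clustered on the couple. A couple-level outcome also needs a coding rule for visits after a break-up or with one partner missing. One option is to keep the enrolled pair as the unit, impute the missing partner's components and then derive CR-HIV; that choice is separate from the power correction.
- **If the individual:** define an individual CR-HIV in section 8.11, reword the hypothesis in section 8.1, and restate section 11.3 for an effective sample size of about 81 (h .35–.56). The 200-participant conclusion still has to go.

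In both cases, say whether the stated N is before or after attrition and the design effect. The cost is revised wording, one coding rule if the couple is chosen, and a re-run power table. No participants, visits or data are added; the stated detectable effects become less favourable.

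### The worst-case power assurance in section 11.3 (about 10% base risk, very high correlation) comes from a pooled-variance formula and does not carry over to the planned sandwich-SE log-odds analysis

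*Combined protocol and SAP*

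**What the plan says.** Section 11.3 (Original Power Calculations) gives minimum detectable effects for 100 couples: "ORs ranged from 0.17 to 0.56, raw proportion differences ranged from 6.6% to 20.5%, and standardized proportion differences (h) ranged from .27 to .42". They are computed on an effective sample of 149 participants, after 20% attrition and a design effect of 1.07.

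The revised calculation supports the smaller trial. It says "We repeated the power analysis approach utilized in our proposal submission", with "power=0.80, 4 post-baseline measurements" and base proportions from 0.10 to 0.50. It adds that "The within-subject correlation for repeated measures was allowed to vary from 0.20 to 0.80". It prints no revised odds ratio, difference or h. Its conclusion for the worst corner, which also has a participant's visits very highly correlated, is in words only: the plan asserts there that "a medium-to-large effect size is still detectable". The same section takes h = 0.20, 0.50 and 0.80 as small, medium and large, and closes by recording approval by the DSMB and the NIMH sponsor.

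Section 8.13 makes the primary analysis a time-averaged arm comparison by logistic GEE. Alpha "will be set at .05 for this planned comparison", and inference uses robust "standard errors to obtain correct inferences even if the chosen correlation structure remains slightly misspecified". The section does not name the test statistic (Wald or score) and gives no rule for an arm with no events.

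**The concern.** A power formula is useful only if its variance resembles that of the test to be run. Near 10% base risk, a medium effect means almost no events in the intervention arm. There, a log-odds variance built on the pooled proportion stays moderate, while the variance that a sandwich estimator targets, built from each arm's own proportion, becomes very large. The two formulas then give opposite answers about detectability.

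The sentence is the section's worst-case reassurance for cutting the trial from 100 to 54 couples. If control-arm CR-HIV is near the low end of the plan's own range, a large true reduction could end as a non-significant or non-estimable log odds ratio and be read as no efficacy.

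**Working it through.** **Inputs.** From 11.3: alpha 0.05 (taken as two-sided), power 0.80, M = 4 visits, base risk P0 0.10–0.50, within-person correlation rho 0.20–0.80, 20% attrition, design effect 1.07, equal allocation. Enrolment is 54 couples (8.3, 11.1). Participants are counted as 11.3 counts them. Write f = (1 + 3·rho)/4, so f = 0.85 at rho = 0.8.

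**1. Reproduce the printed ranges.** Use n = 149/2 = 74.5 per arm and solve

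logit(P0) − logit(P1) = 2.80 × √{2f / [n·p̄(1 − p̄)]}, with p̄ the mean of P0 and P1.

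Over the grid this gives OR 0.166–0.556, difference 6.6–20.4% and h 0.275–0.419. The printed values are 0.17–0.56, 6.6–20.5% and 0.27–0.42. The other variants miss. Averaging the two arms' p(1 − p) gives a lowest OR of 0.161 and h up to 0.429; control-arm variance alone gives a lowest OR of 0.244. At P0 = 0.10, rho = 0.8, difference-based, arcsine and mixed log-odds formulas give OR 0.053–0.119, and the fully unpooled log-odds test never reaches 80%.

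**2. Sample sizes for the revised claim.** Fifty couples with no deductions give 50 per arm. Fifty-four couples after deductions give 108 × 0.8 / 1.07 = 80.7, or about 40 per arm.

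**3. What h means at P0 = 0.10.** h = 2·arcsin√P0 − 2·arcsin√P1. Its maximum, at P1 = 0, is 2·arcsin√0.10 = 0.644, so the plan's large benchmark of 0.80 is impossible for a reduction. h = 0.5 means P1 = 0.0051, and h = 0.6 means P1 = 0.0005. At h = 0.5 with 50 per arm, the intervention arm expects 50 × 4 × 0.0051 ≈ 1 event over all visits.

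**4. Pooled against unpooled, P0 = 0.10, rho = 0.8, n = 50, h = 0.5.** The log-odds difference is 3.07.

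- Pooled: p̄(1 − p̄) = 0.0498; SE = √(1.7/(50 × 0.0498)) = 0.83; z = 3.71; power 96%.
- Unpooled, variance (f/n)·[1/(P0·Q0) + 1/(P1·Q1)], Q = 1 − P: 0.017 × (11.1 + 195.6) = 3.51; SE = 1.87; z = 1.64; power 37%.

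Unpooled power peaks at P1 ≈ 0.011: 0.017 × (11.1 + 91.1) = 1.74; SE = 1.32; z = 2.29/1.32 = 1.74; power 41%. With n = 40 the peak is 34%.

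**5. Simulation** (20,000 trials per cell, four exchangeable visits, no covariates, complete data, P0 = 0.10, rho = 0.8):

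| | 50 per arm | 40 per arm |
|---|---|---|
| Pooled formula, h = 0.5 | 96% | 91% |
| Unpooled log-odds Wald, h = 0.5 (formula) | 37% | 31% |
| Unpooled log-odds Wald, best over all P1 (formula) | 41% | 34% |
| Trials with no intervention-arm events, h = 0.5 | 70% | 75% |
| Sandwich Wald, h = 0.5, those trials counted as non-significant | 12% | 7% |
| Robust score / risk-difference Wald, h = 0.5 | 74–75% | about 60% |
| Robust score / risk-difference Wald, h = 0.6 | 84–85% | 68–70% |

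**6. Where it stops.** With 40 per arm and h = 0.5, the robust score test has about 79% power at rho = 0.5 and 94% at rho = 0.2. At P0 = 0.5, formula and simulation differ by less than about 3 points.

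**The case against.** Several points against the concern are sound.

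- **The sponsor's arithmetic is not wrong.** The printed ranges reproduce, and the same formula carried to the smaller sample does support the sentence (detectable h of 0.43 at 100 participants, 0.46 at 80). The formula is inferred: 11.3 names only a software module.
- **Section 8.13 never says Wald.** Sandwich standard errors point that way, but a robust score test also fits the text.
- **The simulated Wald figures of 7–12% depend on a scoring rule that the plan does not contain.** In a couple-clustered version of the simulation at h = 0.5, power was 29–41% among estimable trials. It was 82–83% if the nominal p-value of a separated fit is accepted. That last reading is not valid inference, but it shows that the result would turn on software behaviour. The 41% and 34% ceilings come from the formula and need no such rule.
- **The sentence can be true on one reading.** If 100 participants is already the number after attrition and design effect, the score test reaches about 84% at h = 0.6. The revised text does not say which it is.

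A reader might infer that the planned analysis has only about 5–15% power whenever base risk is near 10%, or that no test can exceed about 70% after attrition. The documents support neither. The first needs rho near 0.8, an effect near h = 0.5 and the scoring rule above. The second holds for Fisher, robust score and risk-difference Wald tests. An optimal size-controlled test still reaches about 80–85% after attrition if intervention risk falls to exactly zero, though only about 65–71% at h = 0.5.

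**Conclusion.** The concern holds as a conditional one. At base risk near 10% and rho near 0.8, the assurance in 11.3 states a property that a log-odds Wald test with sandwich standard errors does not have. Power is at most about 41% with 50 per arm, or 34% with 40, whatever the reduction. Conventional alternatives come close to or pass 80% only with 50 analysable per arm and near-elimination of risk. After the plan's own deductions they reach about 60% at h = 0.5 and 68–70% at h = 0.6. A large effect by the plan's benchmark cannot occur there at all.

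This rests on the inferred formula, two-sided 0.05, exchangeable correlation, complete data and participants as the unit. It does not show that the trial is underpowered across the 10–50% range. Section 8.11 defines CR-HIV per couple, so participant-based figures may not describe the final test either. With 20–25 couples per arm, even an optimal couple-level test has only 32–44% at h = 0.5 in this corner.

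**What to change.** (a) In 11.3, replace the worst-case sentence with power simulated for the actual primary test at the 54 couples to be enrolled, after the plan's attrition and clustering, using the same analysis unit as the primary outcome. Say whether each N is before or after those deductions. State that, after attrition, with control risk near 10% and rho near 0.8, conventional tests do not reach 80% power for a medium (h = 0.5) or larger reduction.

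(b) In 8.13, prespecify the generalised (robust) score test for the primary arm contrast, and report the risk difference with its interval beside the odds ratio. An arm with few or no events then still gives a usable test. The statistician should confirm that the score statistic is available with the alternating logistic regression option.

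Cost: a short simulation, wording changes in two sections and a less favourable stated power. No extra participants, visits or data are needed.
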